- **Data Management.** In the initial 3 months, data management procedures will be developed and implemented. Data entry and quality assurance will be ongoing during enrollment, with validation and double-entry procedures in place to ensure accurate data entry. Study staff will be trained to limit missing data by checking questionnaires

immediately and prompting for additional response and re-contacting participants if necessary. Study staff will attempt to collect all post-randomization data regardless of treatment attrition.

- **Statistical Analysis.** Data analysis will occur in a staged approach, moving from initial descriptive analyses to hypothesis tests. Descriptive statistics and plots will summarize and assess distributional properties of key variables. Randomized groups will be compared on baseline demographic and clinical variables using analysis of variance, 2, or Wilcoxon-rank sum tests. Any baseline variables potentially confounded with treatment condition will be incorporated in the primary analyses as covariates. Outliers will be assessed and variables whose distributions depart significantly from normality will be transformed.

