- **Missing Data.** The primary outcome will be tested using an intent-to-treat framework. If, the extent of missing data is small and the data appear to be consistent with a missing-at-random model (MAR) [84], then the maximum likelihood analysis using all randomized cases and the observed data is an appropriate method for handling the missing data [85]. In the MAR model the missingness can be a function of the observed covariates and observed outcomes. If the missingness is related to the unobserved outcome, then the missing values are considered missing not at random (MNAR). However, the MAR assumption has been shown to be plausible even in studies such as substance abuse in adolescents [86]. The critical element when conducting MAR-based analyses is to include covariates related to the missingness in the statistical model [87]. As a check on the sensitivity of our conclusions to the assumption that the missing data are MAR we will conduct pattern-mixture modeling, which is appropriate with data is likely MNAR [88, 89]. In these models participants are categorized into groups based on patterns of missing data over time. Missing data pattern groups are then included as covariates in the statistical model and the effect of missing data on parameter estimates can be determined. Parameter estimates can be averaged over the missing patterns to adjust for biased estimates.

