- **Power analysis:** We determined sample size for a two group design with PHDD as the primary outcome at post-treatment. A recent meta-analysis comparing the effects of TOP compared to placebo on heavy drinking found an overall standardized effect size of .406 [5]. The overall effect size was determined from seven studies with effect sizes ranging from .140 to .623. To ensure adequate power we calculated a sample size for a two-sample t-test by condition. The proposed primary analysis uses PHDD measured at baseline, post-intervention, 3, and 6 months in a random-intercepts regression model; however this use of additional data should serve to increase the power. A two-tailed test would require a sample size of 192 participants to detect an effect size of .406 with 80%. This is not a feasible sample size to recruit within the study's recruitment window. Alternatively, a 1-tailed test requires a sample size of 120 to have 72% power to detect the expected effect size. A one directional test is warranted given we are interested only in the improvement of PHDD for the TOP condition compared to the placebo condition. In addition, a sample size of N = 120 provides 80% power for a two-tailed test to detect a sample size of .516, a somewhat larger effect size within the range of effect sizes pooled in the recent meta-analysis [5]. Overall, we believe a sample size of N = 120 balances three needs: (1) sufficient power to compare the study groups; (2) the reality of recruiting a sample of Veterans with AUD and PTSD; and (3) overall project cost considerations.

Aims:

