- **Primary Aim Analysis.** As stated in Aim 1, we will evaluate the efficacy of PE+TOP, as compared to PE+PLA, in percent heavy drinking days (PHDD) among Veterans with comorbid AUD/PTSD at post-treatment and 3- and 6-month follow-up. The statistical model will be a generalized linear mixed model with a log link and gamma distribution variance function. If the over-dispersion parameter is close to zero a Poisson regression model will also provide equivalent model fit. The model will include a factor for treatment condition (PE+TOP, PE+PLA) and a linear term for time (baseline, post-treatment, 3, and 6 month follow-up). This model can be expanded to determine an adjusted intervention effect by including covariates such as gender and era of service. The primary test of treatment effect will be a group x time interaction. This flexible analytic method provides maximum likelihood parameter estimates based on all of the available data, allowing for the inclusion of cases with missing data and the modeling of the covariance error structure of the data across the

assessment points [90]. If the extent of missing data is small and the data appear to be consistent with a missing-at-random model, we will also carry out maximum-likelihood based on a “completer-analysis” using the observed data.

- **Secondary Aim Analyses.** As stated in Aims 2 and 3, veterans in PE+TOP, compared to PE+PLA, will show greater improvements in PTSD, depression symptoms, functional impairment and quality of life at post-treatment and 3- and 6-month follow-up. We will first examine the relationships among these outcomes to determine if composite scores should be created from highly correlated variables. This will help to reduce the number of statistical tests. The statistical model for these analyses will be random effects regression models as described in the primary aim analysis section, using identity link for Gaussian distributed linear variables and log or logit link functions for discrete or skewed outcome variables. These analyses would be in an intent-to-treat framework using maximum likelihood as before.

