Alcohol and Substance Use Measures. At baseline, participants will be administered the AUD and SUD sections of the Structured Clinical Interview for DSM-5 [SCID; 52]. The Timeline Follow-back Procedure [TLFB; 63] will be employed at all assessment points to evaluate drinking and drug use during the 90 days preceding the screening visit. The Quantity-Frequency Index [64] and maximal consumption will be calculated for alcohol use. Drug use indices will be similarly derived for other drugs. The TLFB will be used at each follow-up to establish: % heavy drinking days (HDD), % days abstinent (PDA), time to relapse to heavy drinking, length of use episodes, severity of relapse, and current alcohol/drug use pattern. The Addiction Severity Index-5th edition (ASI) interview [65] which includes seven subscales (medical, employment, alcohol use, drug use, legal, family/social, and psychiatric), will be used to assess severity of alcohol problems. A self-report Substance Use Inventory [SUI; 66] will be administered at treatment sessions. It asks on which of the preceding seven days participants used alcohol or any of seven major types of drugs. Participants will complete an initial toxicology screen at baseline and random screens will be conducted during 25% of the assessment. Relapse episodes will be classified using the Modified Contextual Cue [MCC; 67] system for precursors using transcribed verbatim reports of relapse episodes, and using Shiffman and Wills' framework of temptation, stress, or other [68]. Craving will be measured weekly using the Penn Alcohol Craving Scale [PACS; 69]. The PACS is a well validated five-item, self-report measure that includes questions about the frequency, intensity, and duration of craving, the ability to resist drinking, and asks for an overall rating of craving for alcohol for the previous week. The PTSD-specific Alcohol Expectancies Questionnaire [P-AEQ; 46] measures alcohol expectancies related to PTSD symptoms. The instrument differentiates between alcohol dependent and non-alcohol dependent

individuals with PTSD, and has good psychometric properties.

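### The primary model for percent heavy drinking days rests on three statements that no single model satisfies, and no rule is given for visits with zero heavy drinking days

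*Combined protocol and SAP*

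**What the plan says.** The model is in Section 9, Primary Aim Analysis. Three statements there describe it:

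- Family and link: "The statistical model will be a generalized linear mixed model with a log link and gamma distribution variance function".
- Limit: "If the over-dispersion parameter is close to zero a Poisson regression model will also provide equivalent model fit".
- Estimation: the method is said to give "maximum likelihood parameter estimates based on all of the available data".

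The primary test is the group by time interaction, with time entered as a linear term. The Power analysis paragraph describes the same outcome as "measured at baseline, post-intervention, 3, and 6 months in a random-intercepts regression model". A negative binomial model is never named, and nothing says how a visit with PHDD of zero is handled. The nearest general rule, in the Statistical Analysis paragraph, is that "variables whose distributions depart significantly from normality will be transformed".

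On the denominator, Section 9.8 says the Timeline Follow-back (TLFB) is "employed at all assessment points to evaluate drinking and drug use during the 90 days preceding the screening visit", and that it yields the percentage of heavy drinking days at each follow-up. Section 9.8 also lists a short form on time spent in a constrained environment since the last visit. No rule connects that form to PHDD.

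**The concern.** The three statements cannot all be true of one model for PHDD. An analyst following the text has to decide which to set aside, possibly after outcome data have accumulated. The options differ in whether visits with no heavy drinking enter the analysis, and those visits are the best outcomes in the trial.

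Inclusion criterion 9 in Section 10 requires participants to be reducing or stopping drinking, or planning to, so some post-baseline zeros should be expected. If they are dropped, records are selected by the value of the outcome itself, and the stated use of all available data no longer holds. The size and direction of the resulting bias depend on how zeros are split between the arms.

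**Working it through.** **1. The plan's own figures.** The Power analysis figures are for a two-sample t-test, with alpha not stated and 0.05 assumed here. They reproduce.
- Per arm, 2 × (1.960 + 0.842)² / 0.406² = 95.2, rounded up to 96, so N = 192.
- One-sided power at 60 per arm: 0.406 × √30 − 1.645 = 0.579, giving 71.9% (stated as 72%).
- Two-sided detectable effect at 60 per arm with 80% power: 0.516.

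None of these depends on the model below, and no figure is stated for that model.

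**2. The Poisson limit.** Gamma variance is φμ². Negative binomial variance is μ + αμ². At μ = 20, where the Poisson variance is 20:

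| Dispersion | Gamma | Negative binomial |
|---|---|---|
| 1 | 400 | 420 |
| 0.1 | 40 | 60 |
| 0.001 | 0.4 | 20.4 |

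The gamma variance goes to 0 and the negative binomial variance goes to 20. The Poisson sentence is therefore true of a negative binomial and false of a gamma.

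**3. A zero under a gamma likelihood.** The density is proportional to y^(k−1)·exp(−ky/μ). At y = 0 the log-density is +∞ for shape k = 0.5, −∞ for k = 2, and finite only at k = 1 exactly. A visit with PHDD of zero makes no usable contribution.

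**4. The readings side by side.**

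| Reading | Fits the gamma wording | Poisson sentence true | Maximum likelihood | Uses zero visits |
|---|---|---|---|---|
| Gamma likelihood | yes | no | yes | no |
| Negative binomial | no | yes | yes | yes, on counts with a day offset |
| Gamma-variance quasi-likelihood | yes | no | no | yes |

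No row satisfies everything the plan states.

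**5. Where zeros can occur.** Inclusion criterion 5 in Section 10 requires at least 20 heavy drinking days in 90: 20/90 = 22.2%. It also requires at least 4 in the 30 days before screening. Baseline is therefore non-zero for everyone, and zeros can arise only at post-treatment, 3 months and 6 months.

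**6. Effect of dropping zeros at one visit.** Let z be the share of zeros in an arm and r the topiramate/placebo ratio of means among non-zero values. The true mean ratio is R = r(1 − z_top)/(1 − z_pla). A positives-only model targets r. The share of the log effect lost is 1 − ln r / ln R. All zero rates and values of r are assumed.

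| Zeros placebo / topiramate | r | R | Consequence of dropping |
|---|---|---|---|
| 5% / 15% | 0.90 | 0.90 × 0.85/0.95 = 0.805 | 1 − 0.105/0.217 = 51% lost |
| 2% / 4% | 0.80 | 0.80 × 0.96/0.98 = 0.784 | 1 − 0.223/0.244 = 8% lost |
| 10% / 10% | 0.80 | 0.800 | none |
| 15% / 5% | 0.80 | 0.80 × 0.95/0.85 = 0.894 | 0.223/0.112, log effect about doubled |

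With full follow-up each arm has 60 × 3 = 180 post-baseline records, so the first row means 9 and 27 zero records.

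**7. The planned interaction.** A simulation used assumed inputs: 400 data sets per case, 60 per arm, four visits of 90 days, and random-intercept maximum likelihood. It compared a gamma model with zeros dropped against a negative binomial with zeros kept.
- 5%/15%, r = 0.90: mean interaction −0.044 against −0.074, or 41% smaller.
- 10%/10%, r = 0.80: −0.086 against −0.075.
- 15%/5%, r = 0.80: −0.081 against −0.036.

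The middle case shows that the two families differ even with equal zero rates, so the 41% cannot be put down to dropping zeros alone.

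**8. Standard errors.** In the null case of the same simulation (10%/10%, r = 1), the negative binomial interaction had an actual SD of 0.037. The median robust SE was 0.037 and the median model-based SE was 0.063. One-sided rejection at a nominal 5% was 6.0% with robust errors (Monte Carlo ± 2.3 points) and 0.3% with model-based errors.

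**9. Denominator.** The only look-back given is the 90 days before screening. Treatment lasts 16 × 7 = 112 days, so at post-treatment a 90-day window would leave out 112 − 90 = 22 days, while a window covering all of treatment would be 112 days. Counts from unequal windows are comparable only with an offset.

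**The case against.** The strongest defence is that the plan refers to a gamma variance function, not a gamma likelihood, and that its next sentence describes a parameter with a Poisson limit. Both phrases can be read as pointing to models that keep zeros, and on those readings no record is lost and none of the bias in step 6 arises. This stands as far as consequences go. A reader might infer that the primary test cannot be run once a zero occurs; the documents do not support that, because two of the three readings run. What they show is an unresolved choice, since each reading that keeps zeros contradicts another statement in the same paragraph.

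Three other stronger inferences also fail:

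- A reader might say that dropping zero visits contradicts the Missing Data commitment to a "maximum likelihood analysis using all randomized cases and the observed data". Every participant has a non-zero baseline, so no randomized case would be lost. Only the all-available-data statement in the Primary Aim Analysis is contradicted.
- A reader might call the dropped zeros missing not at random in the Missing Data paragraph's sense. That definition concerns outcomes that were not observed. A PHDD of zero is observed, and excluding it is selection on the outcome by the analyst.
- A reader might say the plan has no day denominator. Section 9.8 gives 90 days before screening. What is open is the post-baseline look-back and the treatment of constrained-environment days.

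It is also fair to say that the negative binomial is not the only sound repair. The general transformation sentence does not settle matters, since it gives neither a trigger nor a constant for zeros.

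**Conclusion.** The primary model statement is internally inconsistent and should be corrected. That conclusion follows from the Primary Aim Analysis paragraph and the form of the two variance functions, and it needs no assumption about zero rates.

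The size of the consequence is conditional. It applies only if the literal gamma reading is followed, and it depends on zero rates that the documents do not give. Under the assumed rates it runs from no bias in the mean ratio, through 8% and 51% of the log effect lost, to the log effect about doubled. Neither direction nor magnitude can be predicted, and the one-visit ratios are not the planned interaction. This is a should-fix defect of specification: the choice of reading ought to be made before anyone can see which one favours a result.

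**What to change.** Before unblinding, replace the gamma and Poisson sentences with one named model and one estimation method, and state that all visits with zero heavy drinking days are kept with no constant added. Either of these would do:

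- **Closest to the text:** a negative binomial mixed model on the number of heavy drinking days, with log link, offset log(TLFB days assessed) and robust standard errors. This keeps the log link and maximum likelihood, and makes the Poisson sentence true. It ignores the cap at days assessed, so a beta-binomial mixed model could be named as a sensitivity analysis.
- **Also acceptable:** a log-link model with gamma variance, fitted by quasi-likelihood or estimating equations with robust standard errors. The Poisson sentence must then be deleted, and the maximum likelihood wording revised together with the missing-data argument that rests on it.

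In either case, state the TLFB look-back at each post-baseline visit and whether constrained-environment days count as days assessed.

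The cost is SAP rewording and minor analysis work. The TLFB day counts and the constrained-environment form are already collected.

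### The primary model treats baseline PHDD as an outcome with a free arm difference, which is valid but gives up precision that baseline adjustment would recover

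*Combined protocol and SAP*

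**What the plan says.** All places are in Section 9 (Design and Methods) of the combined protocol and SAP, under the statistical headings.

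- **Primary Aim Analysis.** The model is a generalised linear mixed model with log link and gamma variance. Its fixed part reads "The model will include a factor for treatment condition (PE+TOP, PE+PLA) and a linear term for time (baseline, post-treatment, 3, and 6 month follow-up", and "The primary test of treatment effect will be a group x time interaction". Covariates are optional; gender and era of service are the examples given, and baseline PHDD is not named.
- **Power analysis.** The same model is described as follows: "The proposed primary analysis uses PHDD measured at baseline, post-intervention, 3, and 6 months in a random-intercepts regression model". The text expects the extra measurements to raise power but does not quantify this. Sizing itself is simpler: "To ensure adequate power we calculated a sample size for a two-sample t-test by condition", with the result that "a 1-tailed test requires a sample size of 120 to have 72% power to detect the expected effect size".
- **Statistical Analysis.** Baseline variables enter the primary analyses as covariates only when they look confounded with arm after randomisation.
- **Secondary Aim Analyses.** For PTSD, depression, functioning and quality of life: "The statistical model for these analyses will be random effects regression models as described in the primary aim analysis section".

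No correlation between baseline and follow-up PHDD, and no SD at either time, is given.

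**The concern.** In a randomised trial the two arms share one baseline mean before treatment. A model with a condition main effect, linear time from baseline and a condition-by-time term estimates a separate baseline mean for each arm, so part of the baseline information goes on a difference already known to be zero in expectation. In the two-visit case this makes the test a comparison of unadjusted changes. In the four-visit case it makes it a comparison of slopes with free intercepts. Either way, the correlation between a participant's baseline and later drinking is not fully used.

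This matters more here than in a comfortably sized trial. The Power analysis says the two-sided requirement of 192 cannot be recruited, and it settles on 120. Precision available from values already collected should not be left unused.

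**Working it through.** **Inputs.** From the documents: 60 per arm (Section 10, 1.a), d = 0.406, one-tailed test. Assumed: alpha 0.05 (not stated, but it reproduces the plan's figures), no dropout, correlation ρ from 0.3 to 0.7, and equal SDs at all visits except in step 4. The calculation is normal-theory with an identity link and compound symmetry, so it only approximates the log-link gamma model.

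**Step 1. The plan's own figure.** z = d√(n/2) = 0.406 × √30 = 2.224. Power = Φ(2.224 − 1.645) = Φ(0.579) = 71.9%, against 72% stated (noncentral t: 71.4%). The stated 192 for 80% two-tailed power and the detectable effect of .516 also reproduce.

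**Step 2. One follow-up visit.** In units of the follow-up variance, unadjusted change has variance 2(1 − ρ) and the baseline-adjusted difference has 1 − ρ². Power = Φ(2.224/√variance − 1.645).

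| ρ | Change: variance, power | Adjusted: variance, power | Gap (points) |
|---|---|---|---|
| 0.3 | 1.40, 59.3% | 0.91, 75.4% | 16 |
| 0.5 | 1.00, 71.9% | 0.75, 82.2% | 10 |
| 0.7 | 0.60, 89.0% | 0.51, 92.9% | 4 |

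At ρ = 0.5 the variance ratio is 0.75, so a change analysis would need 120/0.75 = 160 participants to match 120 with adjustment.

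**Step 3. The planned test: condition by linear time over four visits.** Code visits 0, 1, 2, 3 (mean 1.5, Sxx = 5) and take ρ = 0.5, with 2/n = 1/30.

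- *Free baseline difference.* Var(b) = (2/n)(1 − ρ)/Sxx = (1/30)(0.5/5) = 0.00333, SE 0.0577.
  - Effect growing linearly to 0.406 at 6 months: slope 0.406/3 = 0.1353, z = 2.34, power 76%.
  - Effect of 0.406 from post-treatment onward: fitted slope 0.3 × 0.406 = 0.1218, z = 2.11, power 68%.
- *Common baseline mean.* Setting the intercept difference a to zero replaces b by b − [Cov(a,b)/Var(a)]a.
  - Var(a) = (2/n)[ρ + (1 − ρ)(1/4 + 1.5²/5)] = (1/30)(0.85).
  - Cov(a,b) = −(2/n)(1 − ρ)(1.5/5) = −(1/30)(0.15).
  - The variance becomes (1/30)(0.1 − 0.15²/0.85) = 0.00245, SE 0.0495.
  - Linear growth: z = 0.1353/0.0495 = 2.73, power 86%.
  - Sustained effect: the free fit has a = 0.75d − 1.5 × 0.3d = 0.3d, so the slope is 0.3d(1 + 0.15/0.85) = 0.353d = 0.1433, z = 2.89, power 89%.

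Coding time in months (0, 4, 7, 10) gives 75% vs 87% for linear growth and 72% vs 92% for a sustained effect. Across both codings, a sustained effect gives 56-60% vs 90-91% at ρ = 0.3 and 86-89% vs 95-96% at ρ = 0.7. Linear growth (0-3 coding) gives 63% vs 82% and 92% vs 95%.

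**Step 4. Unequal SDs.** Let k be the baseline SD divided by the follow-up SD. The change variance becomes 1 + k² − 2ρk; the adjusted variance stays 1 − ρ². At ρ = 0.5 and k = 0.8 the change variance is 1 + 0.64 − 0.80 = 0.84, z = 2.224/√0.84 = 2.43, power 78.3%, against 82.2% adjusted: a gap of 3.9 points. It is 1.8 points at k = 0.7 and zero at k = ρ = 0.5. For the slope test at ρ = 0.5 and k = 0.8, with weights that reflect the unequal variances, the gap is about 4 points (linear growth) or 7-8 (sustained).

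**The case against.** The best defence is that this is a conventional longitudinal model and the size of any gain is unknown. Much of that stands.

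- **A fixed ten-point loss.** A reader might take the ρ = 0.5 result as the trial's loss. It rests on an assumed correlation and on equal SDs. Entry requires at least 20 heavy drinking days in 90 (Section 10, inclusion criterion 5), which confines baseline PHDD to roughly 22% and above (20/90) while follow-up can span 0 to 100%. A ratio k below 1 is therefore plausible. It is not established, and k above 1 would widen the gap.
- **A contradiction with the Power analysis.** A reader might infer that the plan's expectation of more power is wrong. The rule that change scores lose to a post-treatment t-test below ρ = 0.5 belongs to the two-visit case with equal SDs. The slope test with a linearly growing effect reaches 76% at ρ = 0.5, above the 72% used for sizing, and equals it near ρ = 0.45. The expectation is not assured at low correlations, but it is not contradicted.
- **Bias through regression to the mean.** A reader might infer that the drinking entry rule distorts the comparison. Regression caused by that rule acts on both randomised arms alike and drops out of the interaction.
- **The imbalance rule already covers this.** It bears on chance imbalance in PHDD, but it is triggered by the data, may never apply to PHDD, and does not remove the free baseline difference. This part of the defence does not stand.
- **Wrong scale.** The figures are not for a log-link gamma model. They indicate direction and rough size only, although a common baseline mean can be imposed under a log link just as well.

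**Conclusion.** The point holds as one of efficiency. The written model is valid under randomisation; the documents give no ground for calling it biased or its expectation of added power false. It does leave baseline information unused. In every equal-SD scenario run, a common baseline mean gave more power.

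Under the assumptions above, the single-visit gain runs from about 16 points at ρ = 0.3 to 4 at ρ = 0.7. For the slope test at ρ = 0.5 it is about 10-11 points with linear growth and 19-21 with a sustained effect. A smaller baseline SD reduces all of these. The loss is measured against an adjusted analysis; it is not a shortfall from the stated 72%.

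**What to change.** In the primary model, and in the Aim 2-3 models that copy it, prespecify a common baseline mean for the two arms: keep time and condition by time, drop the condition main effect, and fit by maximum likelihood with all randomised participants.

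An alternative is to model only the post-treatment, 3- and 6-month values, with the participant's own baseline value as a covariate and a condition effect at those visits. This is not equivalent. With linear time, the first option makes the arm difference grow in proportion to time (on the link scale), which the second does not impose. The second also leaves out participants with no follow-up value. The SAP should name one.

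Neither the written model nor the first option detects an effect that fades to zero by 6 months: at ρ = 0.5 power is 2-4% vs 8-11%. That comes from the linear time term, and this change does not cure it.

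The cost is about one sentence of SAP wording, with no new data, visits or participants.
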